9.3.2 Dosing Visit 2 (Part B)

Doses 3 and 4:

Pre-Dose 3 and 4:

- Evaluation of hydration status (prior to Dose 3 only)
- Vital signs (body temperature, systolic and diastolic BP, HR, RR)
- 12-Lead ECG (prior to Dose 3 only)
- Record the use of supplemental oxygen, method of delivery (eg, nasal cannula), percent O₂/flow rate supplied
- Pulse oximetry on room air (if deemed safe by PI or health care provider)
- RSV Clinical Scoring System every 24 hours (prior to Dose 3 only) ([Appendix 17.1](#))
- Record RSV-related signs and symptoms, and severity every 12 hours (if indicated), including: temperature, cough, coryza, grunting with expiration, nasal flaring, retractions, and wheezing
- Nasopharyngeal swab according to sampling schedule in [Table 4](#) (Pre-Dose 4 sample is optional)
- Concomitant medication review

- Adverse event review
- Study medication administration (Dose 3 and Dose 4)
- The times of the prior feeding and first feeding after dosing should be recorded.

9.3.3 Dosing Visit 3 (Part B)

Dose 5:

Pre-Dose 5:

- Evaluation of hydration status
- Vital signs (body temperature, systolic and diastolic BP, HR, RR)
- 12-Lead ECG
- Record the use of supplemental oxygen, method of delivery (eg, nasal cannula), percent O₂/flow rate supplied
- Pulse oximetry on room air (if deemed safe by PI or health care provider)
- Record RSV-related signs and symptoms, and severity every 12 hours (if subject remains hospitalised), including: temperature, cough, coryza, grunting with expiration, nasal flaring, retractions, and wheezing
- RSV Clinical Scoring System performed every 24 hours ([Appendix 17.1](#))
- Nasopharyngeal swab according to sampling schedule in Table 4
- Concomitant medication review
- Adverse event review
- Study medication administration (Dose 5)
- The times of the prior feeding and first feeding after dosing should be recorded.

Dose 6:

Pre-Dose to 0 Hours:

- Vital signs (body temperature, systolic and diastolic BP, HR, RR)
- Record the use of supplemental oxygen, method of delivery (eg, nasal cannula), percent O₂/flow rate supplied
- Pulse oximetry on room air (if deemed safe by PI or health care provider)
- Record RSV-related signs and symptoms, and severity every 12 hours (if indicated), including: temperature, cough, coryza, grunting with expiration, nasal flaring, retractions, and wheezing
- PK blood sample according to sampling schedule in [Table 5](#)
- Nasopharyngeal swab according to the sampling schedule in Table 4
- Concomitant medication review
- Adverse event review
- Study Medication administration (Dose 6)
 - The times of the prior feeding and first feeding after dosing should be recorded.

1-2 Hours OR 4-5 Hours OR 6-8 Hours Post-Dose 6:

The following assessments will be carried out at either 1 to 2 hours, 4 to 5 hours or 6 to 8 hours Post-Dose 6. The time point chosen (1-2, 4-5 or 6-8 hours) will be defined after PK

analysis of Part A and sites will be notified of the chosen time point in the Dosing Guidance letter.

- Vital signs (body temperature, systolic and diastolic BP, HR, RR)
- 12-Lead ECG
- PK blood sample according to sampling schedule in [Table 5](#)
- Concomitant medication review
- Adverse event review

If a subject is discharged:

The parent/legal guardian (and another caregiver, if required) must be trained on the storage, preparation, and administration of the IMP at home. The parent/legal guardian will be issued with the IMP kit(s) for their child and adequate supplies for preparation and administration of the remaining doses of IMP will be provided. A Treatment Diary Card will be issued that explains how the IMP should be stored and prepared and the parent/legal guardian will be asked to record relevant details of the administration of IMP at home (including date and time). Instructions should also be given on when to return to the clinic for Study Visits.

9.3.4 Dosing Visits 4 and 5 (Part B)

(Doses 7 to 10):

If in-patient:

Pre-Dose 7 to 10:

- Evaluation of hydration status (prior to Doses 7 and 9)
- Vital signs (body temperature, systolic and diastolic BP, HR, RR)
- 12-Lead ECG (prior to Doses 8 and 10)
- RSV Clinical Scoring System performed every 24 hours (prior to Doses 7 and 9)
- Record RSV-related signs and symptoms, and severity every 12 hours (if indicated), including: temperature, cough, coryza, grunting with expiration, nasal flaring, retractions, and wheezing (prior to each dose)
- Record the use of supplemental oxygen, method of delivery (eg, nasal cannula), percent O₂/flow rate supplied (prior to each dose)
- Pulse oximetry on room air (if deemed safe) by PI or health care provider (prior to each dose)
- PK blood sample 12 hours Post-Dose 6 (pre-Dose 7 only) according to sampling schedule in [Table 5](#)
- Nasopharyngeal swab (prior to each dose) according to sampling schedule in [Table 4](#). Pre-Dose 8 and 10 Nasopharyngeal swab samples are optional.
- Concomitant medication review
- Adverse event review
- Study medication administration (Doses 7 to Dose 10)
 - The times of the prior feeding and first feeding after dosing should be recorded.
- In case of discharge: provide parent/legal guardian with treatment diary, patient leaflet, and clear instructions how to administer IMP. An additional nasopharyngeal swab sample

should be taken according to Table 4 if the last nasopharyngeal swab sample was taken > 12 hours prior to the discharge.

9.3.5 Post-Treatment (Part B)

Visit Day 7 (40-48 Hours Post-Dose 10) Follow-Up:

Note: Visit Day 7 may occur on Study Days 7 or 8 depending on when the subject received their first Dose of IMP.

- Physical examination (symptom-directed examination, general condition, lung auscultation, and respiratory muscles retractions)
- Evaluation of hydration status
- Body weight/length/head circumference
- Vital signs (body temperature, systolic and diastolic BP, HR, RR)
- 12-Lead ECG
- Pulse oximetry on room air (if deemed safe by PI or health care provider)
- RSV Clinical Scoring System
- Record RSV-related signs and symptoms, and severity every 12 hours (if indicated), including: temperature, cough, coryza, grunting with expiration, nasal flaring, retractions, and wheezing
- Adapted ReSVinet scale for parental use
- Safety laboratory tests (clinical chemistry and haematology)
- Urinalysis
- PK blood sample according to sampling schedule in [Table 5](#)
- Nasopharyngeal swab according to sampling schedule in [Table 4](#)
- Concomitant medication review
- Adverse event review

Telephone Follow-Up (Day 12):

- Concomitant medication review
- Adverse event review

9.4 Treatment Part C

Ideally all subjects in Part C should remain hospitalised for at least 48 hours post-randomisation to accommodate taking the first 4 doses of IMP and collection of all the assessments scheduled for Dosing Visit 1 and Dosing Visit 2 ([Table 3a](#))

A subject may be discharged from hospital prior to Dosing Visit 3 and be seen as an outpatient provided all of the following requirements are met:

1. The subject is judged by the Investigator or other healthcare provider to be doing well clinically and to warrant hospital discharge,
2. The parent/caregiver can comply with the dosing at home,

3. Adequate provisions are in place for the subject to be seen in an outpatient setting to complete the study procedures and assessments, either at the hospital/clinic as an outpatient or at home (ie, visited by a home health nurse or equivalent). For both outpatient settings, the following assessments and sample collections are required for key study endpoints:
 - a. Administer one dose per Dosing visit or observe parent caregiver doing the same
 - b. Obtain at least one nasopharyngeal swab sample each day (Pre-Dose at Dosing Visits 2, 3 and 4 and 5)
 - c. Obtain PK samples Pre-Dose 6, and at 4-5 hours Post-Dose for either Dose 6 or Dose 7 (depending on the time of day for the doses)
 - d. Obtain an ECG at Post-Dose 6. Depending on the time of day Dose 6 falls the assessments can be moved relative to Dose 7
 - e. Assess the following at each of Dosing Visits 2, 3, 4 and 5
 - Adverse events
 - Concomitant medication review
 - Vital signs
 - Hydration status
 - ReSVinet Score for Clinicians
 - RSV signs and symptoms
 - Supplementary Oxygen
 - Pulse oximetry on room air

Following the outpatient visits on Dosing Visit 3, the parent/caregiver must continue to complete all home dosing and the Adapted ReSVinet scale for parental use assessments on Dosing Visits 4 and 5 as outlined in [Table 3b](#) and must return for Visit Day 7 40-48 hours after the last dose (Dose 10), Visit Day 14 and Visit Day 34. The parent/caregiver will record in the Patient Booklet for doses given at home whether any concomitant medications have been administered and also their assessment of how the child is feeling.

9.4.1 Dosing Visit 1 (Part C)

-2 Hours to 0 Hours Pre-Dose 1:

- Reassess for eligibility against the inclusion and exclusion criteria
- Physical examination
- Evaluation of hydration status
- Vital signs (body temperature, systolic and diastolic BP, HR, RR)
- ReSVinet Scale for Clinicians ([Appendix 17.6](#))
- Record RSV-related signs and symptoms, and severity every 12 hours (if indicated), including: temperature, cough, coryza, grunting with expiration, nasal flaring, retractions, and wheezing

- Record the use of supplemental oxygen, method of delivery (eg, nasal cannula), Percent O₂/Flow rate supplied
- Pulse oximetry on room air (if deemed safe by PI or health care provider)
- Randomisation for Eligible Subjects (stratified by age group)
- Nasopharyngeal swab
- Concomitant medication review
- Adverse Events

Note: If any of the assessments above were carried out within 2 h Pre-Dose 1 for screening purposes, it is not necessary to repeat that assessment for the -2 h to 0 h Pre-Dose 1 timepoint. However, if the assessment was carried out >2 h prior to Dose 1 for screening purposes (i.e. within the first 22 hours of the screening window), the assessment must be repeated between -2 h to 0 h Pre-Dose 1.

Dosing (0 Hours):

- Concomitant medication review
- Adverse event review
- Study medication administration (Dose 1)
 - The times of the prior feeding and first feeding after dosing should be recorded.

+4-5 Hours Post-Dose 1:

The following assessments will be carried out at 4 to 5 hours Post-Dose 1.

- Vital signs (body temperature, systolic and diastolic BP, HR, RR)
- 12-Lead ECG
- Concomitant medication review
- Adverse event review
- PK blood sample according to sampling schedule in [Table 5](#). **Note:** This sample will only be required if the dose level was not previously evaluated in Part B.

12 Hours Post-Dose 1 (Pre-Dose 2):

- Vital signs (body temperature, systolic and diastolic BP, HR, RR)
- Record RSV-related signs and symptoms, and severity every 12 hours (if indicated), including: temperature, cough, coryza, grunting with expiration, nasal flaring, retractions, and wheezing
- Record the use of supplemental oxygen, method of delivery (eg, nasal cannula), Percent O₂/Flow rate supplied
- Pulse oximetry on room air (if deemed safe by PI or health care provider)
- Optional Nasopharyngeal swab according to sampling schedule in [Table 4](#)
- Concomitant medication review
- Adverse event review
- PK blood sample according to sampling schedule in [Table 5](#). **NOTE:** This sample will only be required if the dose level was not previously evaluated in Part B.
- Study Medication Administration (Dose 2)

- The times of the prior feeding and first feeding after dosing should be recorded.

9.4.2 Dosing Visit 2 (Part C)

Procedures and assessments scheduled for Dosing Visit 2 in Part C are required if the subject is currently hospitalised. If the subject has met the criteria for early discharge prior to Dosing Visit 2 and is being seen as an outpatient the required assessments should still be completed and are listed in [Section 9.4](#) and [Table 3b](#). In case of early discharge, provide parent with Patient Booklet, video access link and clear instructions how to administer IMP. An additional nasopharyngeal swab sample should be taken according to Table 4 if the last nasopharyngeal swab sample was taken > 12 hours prior to discharge.

Pre-Dose 3:

- Evaluation of hydration status
- Vital signs (body temperature, systolic and diastolic BP, HR, RR)
- 12-Lead ECG
- ReSVinet scale for clinicians (Part C only, [Appendix 17.6](#))
- Adapted ReSVinet scale for parental use ([Appendix 17.2](#))
- Record RSV-related signs and symptoms, and severity every 12 hours (if indicated), including: temperature, cough, coryza, grunting with expiration, nasal flaring, retractions, and wheezing
- Record the use of supplemental oxygen, method of delivery (eg, nasal cannula), Percent O₂/Flow rate supplied
- Pulse oximetry on room air (if deemed safe by PI or health care provider)
- Nasopharyngeal swab according to sampling schedule in Table 4
- Concomitant medication review
- Adverse event review
- Study Medication Administration (Dose 3)
 - The times of the prior feeding and first feeding after dosing should be recorded.

Pre-Dose 4:

- Vital signs (body temperature, systolic and diastolic BP, HR, RR)
- Record RSV-related signs and symptoms, and severity every 12 hours (if indicated), including: temperature, cough, coryza, grunting with expiration, nasal flaring, retractions, and wheezing
- Record the use of supplemental oxygen, method of delivery (eg nasal cannula), Percent O₂/Flow rate supplied
- Pulse oximetry on room air (if deemed safe by PI or health care provider)
- Optional Nasopharyngeal swab according to sampling schedule in Table 4
- Concomitant medication review
- Adverse event review
- Study Medication Administration (Dose 4)
 - The times of the prior feeding and first feeding after dosing should be recorded.

9.4.3 Dosing Visit 3 (Part C)

Procedures and assessments scheduled for Dosing Visit 3 in Part C are required if the subject is currently hospitalised. If the subject has met the criteria for early discharge and is being seen as an outpatient the required assessments are listed in [Section 9.4](#) and [Table 3b](#). In case of early discharge, provide parent with Patient Booklet, video access link and clear instructions how to administer IMP. An additional nasopharyngeal swab sample should be taken according to Table 4 if the last nasopharyngeal swab sample was taken > 12 hours prior to discharge.

Pre-Dose 5 (All of the assessments to be completed if still an in-patient):

- Evaluation of hydration status
- Vital signs (body temperature, systolic and diastolic BP, HR, RR)
- 12-Lead ECG
- ReSVinet scale for clinicians ([Appendix 17.6](#))
- Adapted ReSVinet scale for parental use ([Appendix 17.2](#))
- Record RSV-related signs and symptoms, and severity every 12 hours (if indicated), including: temperature, cough, coryza, grunting with expiration, nasal flaring, retractions, and wheezing
- Record the use of supplemental oxygen, method of delivery (eg, nasal cannula), Percent O₂/Flow rate supplied
- Pulse oximetry on room air (if deemed safe by PI or health care provider)
- Nasopharyngeal swab according to sampling schedule in Table 4
- Concomitant medication review
- Adverse event review
- Study Medication Administration (Dose 5)
 - The times of the prior feeding and first feeding after dosing should be recorded.

Dose 6 (All of the assessments to be completed if still an in-patient)

Pre-Dose to 0 Hour:

- Vital signs (body temperature, systolic and diastolic BP, HR, RR)
- Record RSV-related signs and symptoms, and severity every 12 hours (if indicated), including: temperature, cough, coryza, grunting with expiration, nasal flaring, retractions, and wheezing
- Record the use of supplemental oxygen, method of delivery (eg, nasal cannula), Percent O₂/Flow rate supplied
- Pulse oximetry on room air (if deemed safe by PI or health care provider)
- PK blood sample according to sampling schedule in [Table 5](#)
- Nasopharyngeal swab according to sampling schedule in Table 4
- Concomitant medication review
- Adverse event review
- Study Medication Administration (Dose 6)
 - The times of the prior feeding and first feeding after dosing should be recorded.

+4-5 Hour Post-Dose 6:

The following assessments will be carried out at 4 to 5 hours Post-Dose 6.

- Vital signs (body temperature, systolic and diastolic BP, HR, RR)
- 12-Lead ECG
- PK blood sample according to sampling schedule in [Table 5](#)
- Concomitant medication review
- Adverse event review

If a subject is discharged:

The parent/legal guardian (and another caregiver, if required) must be trained on the storage, preparation, and administration of the IMP at home. The parent/legal guardian will be issued with the IMP kit(s) for their child and adequate supplies for preparation and administration of the remaining doses of IMP will be provided. A Patient Booklet and video access link will be issued that explains how the IMP should be stored and prepared and the parent/legal guardian will be asked to record relevant details of the administration of IMP at home (including date and time). Instructions should also be given on when to return to the clinic for Study Visits.

See [Section 9.4](#) and [Table 3b](#) for details of assessments required in subjects who are outpatients.

9.4.4 Dosing Visits 4 and 5 (Part C)

(Doses 7 to 10) - All of the assessments to be completed if still an in-patient:

- Evaluation of hydration status (Doses 7 and 9)
- Vital signs (body temperature, systolic and diastolic BP, HR, RR) (prior to each dose)
- 12-Lead ECG (prior to Doses 8 and 10)
- ReSVinet scale for clinicians every 24 hours (Doses 7 and 9) ([Appendix 17.6](#))
- Adapted ReSVinet scale for parental use ([Appendix 17.2](#)). **Note:** To be completed whether hospitalised or discharged.
- Record RSV-related signs and symptoms and severity every 12 hours (if indicated), including: temperature, cough, coryza, grunting with expiration, nasal flaring, retractions, and wheezing (prior to each dose)
- Record the use of supplemental oxygen, method of delivery (eg, nasal cannula), percent O₂/flow rate supplied (prior to each dose)
- Pulse oximetry on room air (if deemed safe by PI or health care provider (prior to each dose)
- Nasopharyngeal swab according to sampling schedule in [Table 4](#). Pre-Dose 8 and 10 Nasopharyngeal swab samples are optional.
- Concomitant medication review
- Adverse event review
- PK blood sample according to sampling scheduled in [Table 5](#). **Note:** This sample will only be required if the dose level was not previously evaluated in Part B.
- Study medication administration (Dose 7 to Dose 10), whether hospitalised or discharged
 - The times of the prior feeding and first feeding after dosing should be recorded.

- In case of discharge: provide parent with Patient Booklet, video access link, and clear instructions how to administer IMP. An additional nasopharyngeal swab sample should be taken according to Table 4 if the last nasopharyngeal swab sample was taken > 12 hours prior to discharge.

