7.2 PART C: Objectives and Endpoints

Primary Objectives for Part C	Primary Endpoint

 • Evaluate the antiviral effects of RV521, compared to placebo, on nasopharyngeal shedding of RSV in infants hospitalised with RSV LRTI 	
 • Time-weighted average change from Baseline to Day 7 in RSV viral load measured in nasopharyngeal swabs by RT-qPCR.
Secondary Objectives for Part C	Secondary Endpoints

 • To evaluate virologic parameters derived from the RSV viral load as measured in nasopharyngeal swabs • CCI [REDACTED] 	
 • Virologic parameters derived from the RSV viral load as measured in nasal swabs include but are not limited to: 
 ○ Change from baseline in viral load (RT-qPCR and CBIA) at each time point ○ Time to below viral load quantification limit (RT-qPCR and CBIA) ○ Proportion of subjects with viral load below quantification limit (RT-qPCR and CBIA) at each timepoint throughout the study • CCI [REDACTED]

 To evaluate the clinical efficacy of multiple oral doses of RV521 in infants hospitalised with RSV LRTI Evaluate the safety and tolerability of RV521 given as a multiple dose regimen 	
 Time to resolution in RSV-related symptoms Time to improvement of RSV-related symptoms Reduction in severity of symptoms by RV521, compared to placebo, measured by a composite score over time Use of supplementary oxygen, including, but not limited to, duration and maximum level of O₂ provided Time to normalisation of respiratory rate Safety of RV521 compared to placebo assessed by incidences of AEs, discontinuations due to AEs, SAEs, and clinically significant changes in laboratory tests

Exploratory Endpoints (Part C)
	
 [REDACTED] [REDACTED] [REDACTED]

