Table 3a. Schedule of Assessments for Part C for subjects hospitalised for a minimum of 3 Dosing Visits

Assessment	Screening	Treatment Phase											Post-Treatment Phase					
	Screening Visit	Dosing Visit 1			Dosing Visit 2		Dosing Visit 3			Dosing Visit 4		Dosing Visit 5		Follow Up				
		Dose 1	Dose 2	Dose 3	Dose 4	Dose 5	Dose 6	Dose 7	Dose 8	Dose 9	Dose 10	Visit Day 7	Visit Day 14±1 Day	Visit Day 34±1 Day				
Time Relative to Dose	-24 to first dose	-2 h to 0 h	0 h	+4-5 h Post-Dose ⁿ						0 h	+4-5 h Post-Dose ⁿ				Last Dose	+40-48 h Post-Dose 10	Day 14	Day 34
Written Informed Consent ^a	X																	
Inclusion / Exclusion Criteria	X	X ^t																
RSV Rapid Diagnostic Test	X ^s																	
Demographics ^b	X																	
Medical History	X																	
Prior Medication Review	X																	
Physical Examination ^c	X	X ^t													X			
Hydration Status ^d	X	X ^t				X		X			X*		X*		X			
Body Weight / Length / Head Circumference	X														X	X	X	
Vital Signs ^e	X	X ^t		X	X	X	X	X	X	X	X*	X*	X*	X*	X	X	X	
12-Lead ECG ^f	X			X		X		X		X		X*		X*	X			
ReSVinet Score for Clinicians ^g	X	X ^t				X		X			X*		X*		X	X	X	
Record RSV Signs and Symptoms ^h	X	X ^t			X	X	X	X	X		X*	X*	X*	X*	X	X	X	
Record Supplemental O ₂		X			X	X	X	X	X		X*	X*	X*	X*				

Assessment	Screening	Treatment Phase												Post-Treatment Phase			
	Screening Visit	Dosing Visit 1			Dosing Visit 2		Dosing Visit 3			Dosing Visit 4		Dosing Visit 5		Follow Up			
		Dose 1	Dose 2	Dose 3	Dose 4	Dose 5	Dose 6	Dose 7	Dose 8	Dose 9	Dose 10	Visit Day 7	Visit Day 14±1 Day	Visit Day 34±1 Day			
Time Relative to Dose	-24 to first dose	-2 h to 0 h	0 h	+4-5 h Post-Dose ⁿ						0 h	+4-5 h Post-Dose ⁿ			Last Dose	+40-48 h Post-Dose 10	Day 14	Day 34
Pulse Oximetry on Room Air		X			X	X	X	X	X			X*	X*	X*	X*		
Adapted ReSVinet Scale for Parental Use ⁱ	X					X		X				X		X	X	X	X
Safety Laboratory Tests (Clinical Chemistry, and Haematology) ^j	X														X ^u		
Urinalysis	X														X ^u		
Randomisation for Eligible Subjects		X															
Pharmacokinetics Blood Sample ^k				X ^{l,n}	X ^l				X ^{l,m}	X ^{l,m,n}	X ^l				X ^{l,m}		
Nasopharyngeal Swab ^o		X			X ^p	X	X ^p	X	X		X ^{q*}	X ^{p*}	X*	X ^{p*}	X	X	X
Concomitant Medication Review	X	X ^t	X	X	X	X	X	X	X	X	X	X	X	X	X	X	X
Adverse Events Review	X	X ^t	X	X	X	X	X	X	X	X	X	X	X	X	X	X	X
Study Medication Administration ^f			X		X	X	X	X	X		X	X	X	X			

Footnotes appear on next page.

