- ^t It is not necessary to repeat the assessment for the -2h to 0 h Pre-Dose 1 timepoint, if the assessment was carried out for screening purposes within the 2 h Pre-Dose 1. However, if the screening assessments were carried out >2 h prior to Dose 1 for screening purposes (i.e. within the first 22 hours of the screening window), the assessment must be repeated between -2h to 0 h Pre-Dose 1.
- ^u Allowed time window on the end of treatment safety bloods and urinalysis is +/- 2 days. Should a subject be discharged after Dose 10, the safety blood sample should be obtained prior to discharge, particularly if the parents/legal guardians are unlikely to return for the next visit.
- ^{*} **Procedure to be done if subject is in the hospital.**

Table 3b. Schedule of Assessments for Part C subjects discharged prior to Dosing Visit 3

Assessment	Screening	Treatment Phase									Post-Treatment Phase		
	Screening Visit	Dosing Visit 1			Dosing Visit 2		Dosing Visit 3	Dosing Visit 4	Dosing Visit 5	Follow Up			
		Dose 1	Dose 2	Dose 3	Dose 4	Doses 5 and 6	Doses 7 and 8	Doses 9 and 10	Visit Day 7	Visit Day 14±1 Day	Visit Day 34±1 Day		
Time Relative to Dose	-24 h to first dose	-2 h to 0 h	0 h	4-5 h Post-Dose							+40-48 h Post-Dose 10	Day 14	Day 34
Written Informed Consent ^a	X												
Inclusion / Exclusion Criteria	X	X ^c											
RSV Rapid Diagnostic Test	X ^b												
Demographics ^d	X												
Medical History	X												
Prior Medication Review	X												
Physical Examination ^e	X	X ^c									X		
Hydration Status ^f	X	X ^c				X ^g		X ^g	X ^g	X ^g	X		
Body Weight / Length / Head Circumference	X										X	X	X
Vital Signs ^h	X	X ^c		X	X	X	X	X ⁱ	X ⁱ	X ⁱ	X	X	X
12-Lead ECG ^j	X			X		X		(X ^k)	(X ^k)		X		
ReSVinet Score for Clinicians ^l	X	X ^c				X		X ^m	X ^m	X ^m	X	X	X
Record RSV Signs and Symptoms ⁿ	X	X ^c			X	X	X	X ^o	X ^o	X ^o	X	X	X
Record Supplemental O ₂		X			X	X	X	X	X	X			

Assessment	Screening	Treatment Phase									Post-Treatment Phase		
	Screening Visit	Dosing Visit 1			Dosing Visit 2		Dosing Visit 3	Dosing Visit 4	Dosing Visit 5	Follow Up			
		Dose 1	Dose 2	Dose 3	Dose 4	Doses 5 and 6	Doses 7 and 8	Doses 9 and 10	Visit Day 7	Visit Day 14±1 Day	Visit Day 34±1 Day		
Time Relative to Dose	-24 h to first dose	-2 h to 0 h	0 h	4-5 h Post-Dose							+40-48 h Post-Dose 10	Day 14	Day 34
Pulse Oximetry on Room Air		X			X	X	X	X	X	X			
Adapted ReSVinet Scale for Parental Use ^p	X					X		X	X	X	X	X	X

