9.4.5 Post Treatment (Part C)

Visit Day 7 (40 – 48 Hours Post-Dose 10) Follow-up:

Note: Visit Day 7 may occur on Study Days 7 or 8 depending on when the subject received his or her first dose of IMP.

- Physical examination
- Evaluation of hydration status
- Body weight/length/head circumference
- Vital signs (body temperature, systolic and diastolic BP, HR, RR)
- 12-Lead ECG
- Record RSV-related signs and symptoms, and severity (if indicated), including: temperature, cough, coryza, grunting with expiration, nasal flaring, retractions, and wheezing
- ReSVinet scale for clinicians ([Appendix 17.6](#))
- Adapted ReSVinet Scale for Parental use ([Appendix 17.2](#))
- Safety laboratory tests (clinical chemistry and haematology)
- Urinalysis
- PK blood sample according to sampling schedule in [Table 5](#)
- Nasopharyngeal swab
- Concomitant medication review
- Adverse event review

Visit Day 14 Follow-up:

- Vital signs
- Body weight/length/head circumference
- Record RSV-related signs and symptoms, and severity (if indicated), including: temperature, cough, coryza, grunting with expiration, nasal flaring, retractions, and wheezing
- ReSVinet scale for clinicians ([Appendix 17.6](#))
- Adapted ReSVinet scale for parental use ([Appendix 17.2](#))
- Nasopharyngeal swab
- Concomitant medication review
- Adverse event review

Visit Day 34 Follow-up:

- Vital signs
- Body weight/length/head circumference
- Record RSV-related signs and symptoms, and severity (if indicated), including: temperature, cough, coryza, grunting with expiration, nasal flaring, retractions, and wheezing

- ReSVinet scale for clinicians ([Appendix 17.6](#))
- Adapted ReSVinet scale for parental use ([Appendix 17.2](#))
- Nasopharyngeal swab
- Concomitant medication review
- Adverse event review

Early Withdrawal (or Discontinuation) Visit

Parents/legal guardians who withdraw their child from the study will be encouraged to allow their child to complete the same final evaluations as subjects completing the study according to this protocol (ie, at the relevant post-treatment visit), particularly safety evaluations.

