10.1.3.10 Other Evaluations

Pulse Oximetry: Pulse Oximetry should be measured for all subjects without oxygen supply if deemed safe. When the SpO₂ is measured, always record the method of O₂ delivery, even if the SpO₂ is measured on room air. Any changes from baseline will be recorded.

Hydration Status: An evaluation of signs of dehydration according to the judgement of the Investigator should be performed ([Appendix 17.5](#) is to be used for reference) and recorded.

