## 8.4. Supplemental Oxygen Use

The number and percentage of subjects with supplemental oxygen use will be presented overall, at baseline and at each post-baseline time point. Reason for use of supplemental oxygen use will also be summarised.

This document is confidential.

Duration of use and overall maximum flow rate of oxygen will be summarised using summary statistics for continuous data. Duration of supplemental oxygen use will be calculated in hours from the start time of first use in the study to the end time of the last use in the study, i.e. ignoring any interruptions, and presented to 1 decimal place.

All tables for Part C, will also be presented by the subgroups defined in Section 6.6.

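### Part C schedules no supplemental-oxygen record after Dosing Visit 5, and SAP 8.4 has no rule for an oxygen course still open at the last record

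*Protocol*

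**What the plan says.** Protocol 7.2 lists as a Part C secondary endpoint: "Use of supplementary oxygen, including, but not limited to, duration and maximum level of O₂ provided".

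Recording is scheduled as follows.
- **Table 3a** (infants hospitalised for at least three Dosing Visits): the row "Record Supplemental O ₂" is marked from before Dose 1 to Dose 10. The marks at Doses 7 to 10 carry the footnote "Procedure to be done if subject is in the hospital". Visit Days 7, 14 and 34 are blank.
- **Table 3b** (infants discharged before Dosing Visit 3): the row is marked through Doses 9 and 10 and is blank afterwards.
- **Section 9.4.4** (inpatients, Doses 7 to 10): "Record the use of supplemental oxygen, method of delivery (eg, nasal cannula), percent O₂/flow rate supplied (prior to each dose".
- **Section 9.4.5**, from "Visit Day 7 (40 – 48 Hours Post-Dose 10) Follow-up" through Days 14 and 34: no oxygen item in any of the three lists.

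SAP 8.4 calculates duration in hours "from the start time of first use in the study to the end time of the last use in the study", ignoring interruptions, and summarises it and the maximum flow rate as continuous data. SAP 8 bases clinical efficacy on observed data without imputation. SAP Table 3, written for a previous Part C design, has the same blanks after Dose 10.

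**The concern.** Oxygen duration needs a stop time. An infant still on oxygen at Dose 10 has no later scheduled assessment at which the stop, a restart or a higher flow would be written down. These are the longest courses, and a drug that shortens illness would be expected to change them. If they are cut at the last record, dropped for lack of an end time, or resolved case by case, the arms will tend to look more alike than they are.

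The gap is also uneven. An infant discharged before Dosing Visit 3 follows Table 3b and is recorded through Doses 9 and 10. An infant discharged after Dosing Visit 3 stays on Table 3a and has no scheduled oxygen record from discharge onwards.

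Neighbouring SAP sections do deal with open durations. SAP 8.3 censors unresolved symptoms at the last record, and SAP 8.5 substitutes the last adverse-event review for a missing discharge. SAP 8.4 has no counterpart.

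**Working it through.** **1. Where scheduled recording ends.** Doses are 12 h apart (Table 3a footnotes), so dose k falls at 12 × (k − 1) h.
- Dose 6: 12 × 5 = 60 h.
- Dose 10: 12 × 9 = 108 h = 4.5 days.
- Visit Day 7: 108 + 40 to 108 + 48 = 148 to 156 h.

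The 60 h and 156 h agree with the viral-load analysis times in Protocol 11.1.3, so the timetable is read correctly.

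**2. Share of follow-up covered.** Study Day 34 is at (34 − 1) × 24 = 792 h. Scheduled oxygen recording covers 108/792 = 14% of that. The remaining (792 − 108)/24 = 28.5 days have none.

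**3. How many courses could be open at 4.5 days.** The documents give no distribution of oxygen duration. As an assumption, take exponential durations counted from Dose 1 with mean m days, so the share open at 4.5 days is exp(−4.5/m).

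| Mean m (days) | Share past 4.5 days | Mean if cut at 4.5 days, m × (1 − exp(−4.5/m)) |
|---|---|---|
| 2 | 11% | 1.79 |
| 3 | 22% | 2.33 |
| 4 | 32% | 2.70 |
| 6 | 47% | 3.17 |

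The SAP's own time course (SAP 3.7: median time to improvement 4 days, interquartile range 3 to 7.5) concerns symptoms, not oxygen, and is not used here.

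**4. What each handling would do to a difference in means**, under the same assumption.
- Open courses cut at 4.5 days: true means of 4 and 3 days (difference 1) appear as 2.70 − 2.33 = 0.37 day. True means of 6 and 4 days (difference 2) appear as 3.17 − 2.70, about 0.46 day before rounding.
- Open courses dropped: the mean of the remainder is m − 4.5 × exp(−4.5/m)/(1 − exp(−4.5/m)). For m = 4 this is 4 − 4.5 × 0.325/0.675 = 1.84. For m = 3 it is 3 − 4.5 × 0.223/0.777 = 1.71. A true difference of 1 day appears as 0.13 day.

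**5. What else is recorded after Dose 10.**
- Clinician ReSVinet item 2 (Appendix 17.6) scores oxygen therapy and positive-pressure support at Days 7, 14 and 34. It gives a status, with no times or flow.
- Appendix 17.4 includes room-air SpO₂, and Protocol 10.1.3.10 says to "always record the method of O₂ delivery, even if the SpO₂ is measured on room air". This gives the method on the day. Section 9.4.5's own list of signs does not name SpO₂.
- Adverse-event review continues at all three visits. It captures events, not oxygen stop times.

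None of these supplies the end time that SAP 8.4 requires.

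**The case against.** The strongest answer is that the oxygen row is not the whole of data capture. SAP 8.4 uses start times, end times and reasons for use, none of which a pre-dose note of method and flow can supply. It therefore implies a fuller CRF oxygen page, and the CRF is not among the documents. That stands: a reader might infer that durations are capped at 108 h by design, but no text sets an end time at Dose 10 or limits the study period to dosing. What remains is that neither document describes such a page or schedules its completion after Dose 10.

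Other stronger readings also go beyond the text.
- *Oxygen is unobserved after Dose 10, or re-use and readmission are missed.* ReSVinet item 2, SpO₂ with delivery method, and AE/SAE reporting give status or event information. A readmission meeting the SAE definition would be reported.
- *Oximetry is dropped at Visit Day 7.* This holds for the separate oximetry row of Tables 3a and 3b. Section 10.1.3.7 counts oximetry among vital signs, which are scheduled then, although the tables' footnote on vital signs omits it.
- *Recording ends with the last dose for infants who stop IMP.* The protocol does not say so. Section 8.5.6.2 keeps infants who stop for a prohibited medication in the study.
- *Maximum level is generally understated.* That needs a peak after Dose 10, for which there is no evidence.

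Two further points are fair. The schedule is the same in every arm, and the proportion on oxygen at each time point during dosing is unaffected. If open courses were simply truncated, the median duration would also survive as long as fewer than half ran past the cut-off. It would not survive if they were dropped, and the SAP does not say which applies.

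**Conclusion.** The point holds as a gap in the schedule and in SAP 8.4. A Part C secondary endpoint depends on oxygen stop times, yet no oxygen record is scheduled after about 108 h, or after discharge during Dosing Visits 4 and 5 under Table 3a. The analysis has no rule for a course still open at that point. Duration is the component at risk; maximum level is affected only by a late peak.

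The likely direction is towards a smaller difference between arms. The size is unknown. The 11% to 47% of courses past 4.5 days, and the shrinkage of a 1-day difference to 0.37 day (cut) or 0.13 day (dropped), rest on assumed exponential durations starting at Dose 1. They also assume that no fuller capture exists. They show what could happen and are not estimates for this trial. Because this is one secondary endpoint and the remedy is cheap, the change should be made, but the primary viral-load analysis does not depend on it.

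**What to change.** **Protocol.** In Tables 3a and 3b and Section 9.4.5, add at Visit Days 7, 14 and 34 an item for supplemental O₂ since the last visit: start and stop date and time, method, and highest flow or percent. Collect it whether or not the infant has been discharged or has stopped IMP. If a CRF oxygen log already holds these fields, name it and schedule its completion to Day 34.

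**SAP.** In the Part C amendment, treat a course still open at last contact as censored. Summarise duration by Kaplan-Meier among infants who used oxygen, and show non-users separately. The SAP has to be amended in any case, because it still describes a 1:1, 120-subject Part C. Protocol 11.1 allows Part C amendments to be signed off before that part's database lock and unblinding.

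**Cost.** One CRF item at three existing visits and a short SAP paragraph, with no new visit or procedure. The downsides are slight recall error for oxygen used at home and a little extra data entry.
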